#### Coping skills

This is measured with the Brief K-COPE a kidney-oriented adaptation of the Brief COPE survey. It has 28 items score 1 to 4. There are 14 subscales composed of 2 items each. The score for each subscale is the sum of the two individual items that compose that scale (2-8).

#### Communication with providers

This is measured with the Communication Assessment Tool (CAT). There are 14 items with a response ranging from 1 to 5. The total score is the average of the 14 items. Question 15 is descriptive and not included in the overall score of the CAT.

*Feasibility Outcomes:* We will perform Wilcoxon rank sum test to test the difference in pre-and post-training knowledge assessments in the mentors (Baseline CHeKS; PLUS vs. 9M and 12 to 18M). The outcome variable for the regression is the difference between pre-and post-training scores and the parameter of interest is the intercept. We will test if the intercept is zero.

For qualitative data, we will review the content of the individual surveys and develop a novel coding scheme to characterize the content including common themes identified. We will also provide descriptive results of the HCCQ survey characterizing mentees' ratings of mentor communication.

---

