## 3 OBJECTIVES AND ENDPOINTS

Table 3.

OBJECTIVES	ENDPOINTS	JUSTIFICATION FOR ENDPOINTS	PUTATIVE MECHANISMS OF ACTION
Primary			
To test the effects of a telephone-based peer mentor intervention on hospital resource utilizations	Composite count of ED visit and hospitalizations at the conclusion of the 12 to 18-month (T2) observation period comparing mentee group to usual care group.	Some visits made by patients on hemodialysis to the ED and subsequent hospitalizations may be avoidable with better outpatient care coordination and patient engagement. Peers may be best suited to provide support for patient activation.	Improvements in patient knowledge, self-efficacy, and skills related to self-care and connecting with their dialysis care team.
Secondary			
1) To test the effects of a mentor peer training program on the uptake of: a) dialysis knowledge and b) mentorship skills.	a) Change in scores on knowledge assessments after training (BL, 9M, 12-18M)  b) Uptake of skills involving	a) Knowledge in mentors is important to then disseminate to mentees through the peer intervention. These skills are in the causal pathway related to adherence behaviors.	Coaching skills by mentors to improve mentee knowledge, self-efficacy, communication skills and perceived social

OBJECTIVES	ENDPOINTS	JUSTIFICATION FOR ENDPOINTS	PUTATIVE MECHANISMS OF ACTION
	motivational interviewing, emotional support, non-judgmental listening and self-efficacy promotion in role playing exercises	b) An established method of training program evaluation includes assessments by the trainer during role playing of mastery of skills by the trainee.	support are hypothesized to increase activation to success in dialysis self-care.

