#### Baseline Visit, 3-Month (Patient participants), 9-Month (Mentor), 12 to 18-Month (T2; All)

Surveys will be completed for all visits by both mentors and patient participants, unless otherwise specified. Mentors will complete baseline surveys prior to participating in training activities.

*Baseline visit.* Include the following assessments:

- Demographics, health literacy, behaviors, and ED/Hospitalization self-reported use
- Self-report of medical history and access to care

*All visits.* Include the following assessments:

- Quality of Life (RAND SF-36)
- Depressive symptoms (CESD-10)
- Dialysis Self-management Self-efficacy (PDialSMS)

- Kidney Disease Self-Management Behaviors Index (KDBI)
- Multidimensional Scale of Perceived Social Support (MSPSS)
- Dialysis-specific Social Support Survey
- Brief Kidney-COPD Survey
- Chronic Hemodialysis Knowledge Survey (CHeKs)
- CHeKs PLUS Survey
- Communication Assessment Tool (CAT)

*Mentee group only – 3-Month Visit.* Include the following assessments:

- Health Care Climate Questionnaire (HCCQ) Long Form
- Checklist for Mentee Assessment of Mentors

*Monthly all participants.* Include the following assessment:

- Self-report of ED visits and/or hospitalizations

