### 9 STATISTICAL CONSIDERATIONS

#### 9.1 STATISTICAL HYPOTHESES

- Primary Endpoint:  
The primary objective is to determine the effectiveness of a peer support telephone intervention compared with usual care to reduce a composite of ED visits and hospitalizations among patients receiving in-center hemodialysis for ESKD. The null hypothesis is that the count of composite events at the end of the study period between intervention and usual care are the same. The alternative hypothesis is that the count of composite events at the end of the study period are different.
- Secondary Endpoint(s):
  - To determine the effectiveness of a peer support phone intervention compared to usual care to improve:
    - dialysis self-management including:
      - Dialysis treatment schedule adherence (mean minutes missed per month)
      - Inter-dialytic weight gain (IDWG) (mean monthly %)
    - nutritional status (serum albumin)
    - dialysis knowledge
    - dialysis self-management self-efficacy
    - social support (general and dialysis-specific)
    - coping skills
    - quality of life
    - communication with providers
- The null hypothesis is that the secondary endpoint values at the end of the study period between intervention and usual care are the same. The alternative hypothesis is that the secondary endpoint values at the end of the study period are different.
- Feasibility endpoint(s):
  - To determine the feasibility of a structured, multicomponent, multiple session peer mentor training program at two sites. There is no specified hypothesis.
  - To determine the acceptance of peer mentor phone intervention by patients. There is no specified hypothesis.

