**Table 4. Scientific Questions to be Addressed with the Trial**

Scientific question	Outcome(s)	Analysis
1. Does phone peer support improve outcomes at 18-months (*12 to 18-months)?	
 
Primary: composite endpoint count of ED visit and hospitalization events
 
Secondary: Various as listed above
 
	Poisson regression with two random intercepts. Random intercepts account for clusters by (1) mentor; (2) dialysis unit  See Section 9.4.2 (Primary); 9.4.3 (Secondary)
2. Is a peer mentor training program feasible?	
 
Attendance records
 
Pre- and Post-knowledge test scores
 
Satisfaction with training
 
Summative assessment
 
	Paired t-tests  Descriptive summaries and content analysis of qualitative data
3. Is a peer mentor training program accepted by patient receiving hemodialysis	
 
Satisfaction with intervention
 
Communication rating of mentors
 
	Descriptive  Content analysis of qualitative data

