#### 9.4.3 ANALYSIS OF THE SECONDARY ENDPOINT(S)

The primary evaluation will be at the end of the study period (12 to 18-months) using all available data regardless of the period end for participants, and comparisons at 3M will be secondary. For the primary evaluation, we will test the longitudinal effect of a peer mentor led telephone intervention on mentee self-management skills including 1) dialysis adherence (mean number of outpatient dialysis hours per month), 2) mean monthly inter-dialytic weight gain (IDWG), and 3) mean monthly albumin levels. We

will compare the rate of change over time of the monthly secondary endpoints between two intervention groups using linear mixed effects regression model. In the regression model, the secondary endpoint (e.g. monthly mean dialysis hours) is the outcome variable with two main effects (the intervention assignment and months from baseline) and the interaction term between the main effects. The interaction term (i.e. the difference in slopes between two groups) is the primary predictor of interest. There will be three random intercepts to account for mentor effect, facility effect (out of seven facilities) and subject effect (to account for within correlation from repeated measurements). We will evaluate differences in baseline variables identified in Table 6 and if they are different between the groups, we will adjust for them as confounders.

For the secondary evaluation at 3M, we will perform Wilcoxon rank-sum test to compare the 3-months change of secondary endpoints between the intervention mentee and control mentees. To account for confounders, we will also fit linear regression model with two random intercepts. In the regression model, the 3 months-change of secondary endpoint is the outcome variable and the intervention assignment of the mentees is the primary binary predictor. The random intercepts will account for the correlation between mentees who share a common mentor as well as the correlation between mentees who are from a common dialysis facility.

Below, each endpoint is described including its source, scoring and planned analysis approach. Additional details for scoring of surveys is provided in the PEER HD Survey Scoring guide document. Within group (mentors) for change in outcomes over time will also be evaluated.

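### Section 9.4.3 names an unpaired test for the mentors' paired knowledge scores, and tests a slope difference where section 9.1 states an end-of-study null for adherence, IDWG and albumin

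*Combined protocol and SAP*

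**What the plan says.** **Mentor knowledge.** The Feasibility Outcomes paragraph of section 9.4.3 says "We will perform Wilcoxon rank sum test to test the difference in pre-and post-training knowledge assessments in the mentors", comparing baseline with 9 months and 12 to 18 months. It continues: "The outcome variable for the regression is the difference between pre-and post-training scores and the parameter of interest is the intercept", with a test that this intercept is zero. Table 4 lists "Paired t-tests" for the same question. Section 8.1 makes the pairing explicit: "Mentors will complete baseline surveys prior to participating in training activities", with the same surveys repeated later. Section 9.4.3 also promises "Within group (mentors) for change in outcomes over time will also be evaluated". Table 3 ranks mentor knowledge change as a secondary endpoint, whereas section 9.1 places mentor training under feasibility and adds "There is no specified hypothesis".

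**Adherence, IDWG and albumin.** Section 9.1 says: "The null hypothesis is that the secondary endpoint values at the end of the study period between intervention and usual care are the same". Section 9.4.3 places the main evaluation at the end of the study, using all available data. It then fits a linear mixed model with arm, month and their interaction, and makes the interaction (the slope difference) the term of interest. The other between-arm analyses named for these endpoints concern the 3-month change. Time is counted in months from baseline, while the adherence endpoint is described as running from month 1.

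**The concern.** The rank-sum test assumes two independent groups. With about 17 mentors (section 5) or 20 (synopsis), discarding the pairing discards much of the information on whether training raised knowledge.

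For the three monthly clinical endpoints, the hypothesis concerns a level at the end and the test concerns a rate of change. Mentoring lasts 3 of 12 to 18 months, and the documents give no expected shape for the effect. If benefit appears early and holds, the arms differ at the end although the slope difference may be small or zero. A reader could then take a null slope test as evidence against the hypothesis in 9.1.

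**Working it through.** The plan gives no power or effect size for these analyses (section 9.2 covers the primary endpoint only), so there is no stated figure to reproduce. Correlations, effect sizes, ICCs and effect shapes below are assumptions.

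**(a) Mentor test.** Of the three descriptions, the intercept test on within-mentor differences is the paired t-test and agrees with Table 4. Only the rank-sum label departs from them.

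An unpaired test treats the variance of the mean change as 2σ²/n; with correlation ρ it is 2σ²(1−ρ)/n. The large-sample type I error is therefore P(|Z| > 1.96/√(1−ρ)). For ρ = 0.3, 0.5, 0.7 the cut-offs are 2.34, 2.77 and 3.58, giving 1.9%, 0.6% and 0.03%. Simulation with 17 mentors (20,000 runs, normal scores) gives about 2%, 0.9% and 0.2%.

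Simulated power for a 0.5 SD gain, two-sided 0.05, at ρ = 0.3 / 0.5 / 0.7:

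| Mentors | Rank-sum | Signed-rank | Paired t |
|---|---|---|---|
| 17 | 25 / 22 / 18% | 35 / 46 / 67% | 37 / 49 / 71% |
| 20 | 30 / 27 / 24% | 42 / 55 / 76% | 44 / 57 / 78% |

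Relative loss with 17 mentors runs from 1 − 25/37 = 32% to 1 − 18/71 = 75%.

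**(b) Slope against end-of-study difference.** Inputs: 73 per arm (section 9.2), two-sided 0.05 (section 9.4.1), residual SD 1, ICC 0.5, mentor and facility variance 0, balanced data. D is the full benefit.

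- The slope difference is the least-squares slope of the effect profile over months. Its SE is √(2/(73·S)), with S = 143 for months 1–12 and 182 for months 0–12.
- The baseline-adjusted month-12 contrast has SE √(2/73 × (2 − 1/2)) = 0.203.
- The baseline-adjusted mean of months 10–12 has SE √(2/73 × (1 + 1/3 − 1/2)) = 0.151.

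Example: benefit building to month 3 then holding, month 0 included, D = 0.5. Slope 0.0586 × 0.5 = 0.0293; SE 0.0123; ratio 2.39; power Φ(2.39 − 1.96) = 67%.

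Power in the right direction with D = 0.5 residual SD:

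| Profile | Slope/month, in D (months 1–12; 0–12) | Slope power (1–12; 0–12) | Month 12 | Months 10–12 |
|---|---|---|---|---|
| Immediate, sustained | 0; +0.033 | 2.5%; 27% | 69% | 91% |
| Builds to month 3, holds | +0.036; +0.059 | 26%; 67% | 69% | 91% |
| Builds to month 6, holds | +0.073; +0.083 | 75%; 92% | 69% | 91% |
| Linear to month 12 | +0.083; +0.083 | 85%; 92% | 69% | 86% |
| Builds to month 3, wanes to D/4 | −0.038; −0.010 | under 1% | 9% | 20% |

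In the last row the intervention arm is better in every month, yet the chance of a significant slope in the wrong direction is 28% (months 1–12) or 6% (month 0 included).

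The scale of D matters. With D = 0.5 total SD (0.5 × √2 = 0.707 residual SD) and month 0 included, slope power is 48% for the immediate sustained benefit, 92% for the build to month 3 and 99.8% for linear growth. The month-12 contrast has 94% in all three.

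Follow-up length also moves the slope: with month 0 included, an immediate sustained benefit gives 0.033D per month over 12 months but 0.016D over 18 (S = 570).

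**The case against.** On (a), the paired intent is clear from the next sentences and from Table 4, and the power loss occurs only if an analyst follows the label and ignores both. That is fair, and it makes this a wording error. The error still needs correcting, because the plan uses rank-sum and Mann-Whitney tests correctly elsewhere for between-arm comparisons, so the label could be followed literally. A reader might infer that the unpaired test risks a false claim that training works. It does not: with positively correlated scores it is conservative.

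On (b), a pre-specified slope model is a legitimate choice, and an end-of-study contrast can be derived from it (arm effect plus interaction times month). That stands, but the plan does not specify that contrast. Three stronger readings are tempting and unsupported:

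- *The two nulls agree only under linear growth from zero.* Every building profile above gives a positive slope on either coding, as does the immediate sustained one once month 0 is included. In those cases both nulls are false in the same direction.
- *The slope test is generally underpowered.* The lowest figures require leaving out month 0, on which the plan is not explicit, and a D of 0.5 residual SD. For gradual growth the slope does as well or better.
- *All survey scores have an end-of-study comparison.* The Quality of life paragraph in 9.4.3 compares arms at the various time points for self-efficacy, social support and quality of life. Knowledge, coping and communication fall under the same 9.1 null but have no named between-arm test at the end of the study.

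**Conclusion.** Both parts hold. (a) The rank-sum test is wrong as written for paired data. Under the assumed gain and correlations, following it would cost about one third to three quarters of the paired t-test's power with 17 mentors, with type I error of about 2% down to 0.2%. How much this matters depends on whether the endpoint is secondary (Table 3) or feasibility without a hypothesis (9.1). (b) The end-of-study null for adherence, IDWG and albumin has no matching test. If the intervention does nothing in any month, both nulls are true, so type I error is not at stake. At ICC 0.5 the slope has no power against an immediate sustained benefit over months 1–12, and 27% (0.5 residual SD) or 48% (0.5 total SD) with month 0 included. The slope mismatch does not touch the primary endpoint, the 3-month comparisons, or the self-efficacy, social support and quality of life scores.

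**What to change.** **(a)** In the Feasibility Outcomes paragraph, replace the rank-sum test with the Wilcoxon signed-rank test or the paired t-test, and name the same test in Table 4.

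**(b)** Choose one of two repairs:

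- Keep the slope model as supporting, and add a baseline-adjusted between-arm contrast from the same mixed model with month as a category, at month 12 or as the mean of months 10–12, as the test of the 9.1 null. The definition should allow for the ±30-day T2 window in section 1.3, because section 1.2 stops monthly record review at T2.
- Restate the 9.1 null as a slope null, if rate of change is the intended question.

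In either case, say whether baseline is a covariate or a month-0 outcome, and what follows if the linearity check in 9.4.2 fails. Extend the time-point comparison in the Quality of life paragraph to knowledge, coping and communication.

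**Cost.** Document wording and slightly more model specification; no new data. If the effect grows gradually, the contrast gives up some power: at ICC 0.5 and 0.5 residual SD, 69% (month 12) or 86–91% (months 10–12) against 92% for the slope with month 0 in the linear and build-to-month-6 profiles. Data after month 12 would serve mainly the supporting slope.

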#### 9.4.4 SAFETY ANALYSES

Adverse events will be descriptively tabulated and included in the analysis report of the study.

---

#### 9.4.5 BASELINE DESCRIPTIVE STATISTICS

All baseline variables will be summarized by treatment group using descriptive statistics (sample size, mean, standard deviation, median, minimum, and maximum) for continuous variables and by the number and percentage of patients for categorical variables. We will test the success of randomization by examining differences in the two treatment groups by performing two-sample Mann-Whitney non-parametric test for continuous variables, and chi-square test for the categorical variables.

This will also include an evaluation of the degree of concordance between mentors and mentees for variables considered for pairing. This includes: sex, race/ethnicity, language, age category and schedule preferences.

---

#### 9.4.6 PLANNED INTERIM ANALYSES

No planned interim analyses.

---

#### 9.4.7 SUB-GROUP ANALYSES

Potential effect modification will be examined by including interaction terms between the intervention and patient characteristics such as sex, race/ethnicity, age, health literacy, numeracy, and depressive symptoms. For baseline factors with statistically significant interactions, intervention effects will be reported by subgroups. This will be applied to all endpoints (primary and secondary).

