## 4 STUDY DESIGN

### 4.1 OVERALL DESIGN

The goal of this study is to test the effects of a peer mentorship program on hospital utilization among high risk patients on hemodialysis as compared to a usual care control group. This is a two-arm pragmatic, randomized at the patient-level controlled trial. Exploratory analyses within the intervention arm will also be performed. Patients will be randomized in a 1:1 allocation and blinded to the research team until the disclosure of the randomization assignment. There will be enrollments in groups until each mentor has been randomly allocated their maximal number of mentees. Randomization will be computer generated and assigned by the coordinating center research team.

This is a multi-site trial, including dialysis units in Bronx, NY and Nashville, TN areas. The collaborating organizations include Albert Einstein College of Medicine (Coordinating Center) and Vanderbilt University Medical Center.

Intervention: Hemodialysis peer mentoring training and telephone coaching program.

The control group will receive kidney disease education about dialysis treatment adherence and access care in alignment with standard of care. Usual care will be at the discretion of the participant's clinical care team.

No interim analyses are planned.

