## 9.2 SAMPLE SIZE DETERMINATION

For evaluation of the primary endpoint, estimates are based on local dialysis unit hospitalization events in the past 12 months. For the control group, we expect 0.27 events per month (100 prevalent patients and 27 composite events per month). With 73 patients per group (after 25% drop-out), our study has >80% power to detect 20% reduction (i.e. a reduction of 0.054 visits per person-month) at type 1 error level 0.05. We will recruit at least 100 patients per group over the course of the study.

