## 9.4 STATISTICAL ANALYSES

### 9.4.1 GENERAL APPROACH

Descriptive statistics will be used to provide for each variable: number of observations, mean, standard deviation, median, minimum and maximum for continuous variables; frequencies and proportions for categorical variables. Results will be reported in accordance with the extended CONSORT guidelines for pragmatic clinical trials using two-sided statistical tests and confidences intervals. For all analyses, the overall level of significance will be set at 0.05. All analyses will be adjusted for site. Adjustment variables will be pre-specified in the following sections. All analyses will be performed using SAS v9.4 (SAS Institute, Cary, NC), STATA (College Station, Tx), or R (currently 3.6.1; <https://cran.r-project.org/>).

Analyses of qualitative data will include content analysis, novel code generations as applicable, interpretation and descriptive reporting.

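### Section 9.4.7 ties the display of subgroup effects to a significant interaction, over an open factor list and all endpoints, which makes false findings likely and biases the displayed effects away from zero

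*Combined protocol and SAP*

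**What the plan says.** The subgroup plan in section 9.4.7 is three sentences long. Interaction terms are to be examined between the intervention and "patient characteristics such as sex, race/ethnicity, age, health literacy, numeracy, and depressive symptoms"; the first words of that phrase leave the list open. The display rule follows: "For baseline factors with statistically significant interactions, intervention effects will be reported by subgroups". The scope comes last: "This will be applied to all endpoints (primary and secondary".

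Section 9.4.1 states "For all analyses, the overall level of significance will be set at 0.05", with reporting "using two-sided statistical tests and confidences intervals". No section describes a multiplicity procedure for the interaction tests. None gives cut points for age, health literacy, numeracy or depressive symptoms, or an expected direction or size of any interaction. Nor does any section commit to reporting interactions that are not significant. Section 9.4.9 applies the exploratory label to intervention dose and mentor-mentee concordance; section 9.4.7 has no such label.

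**The concern.** The rule makes the p-value of the interaction decide whether stratified effects appear. This has two consequences. With many tests at 0.05, some will pass by chance, and those are the ones displayed. And an estimate shown because it crossed a threshold is on average further from zero than the truth; the lower the power, the larger the gap.

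The trial is sized for its main effect, so power for interactions is low. An open list adds a third problem: without a fixed number of tests, nobody can say how many chance findings to expect. At stake are statements about who benefits from peer mentoring, for example by race/ethnicity or depressive symptoms. The test of the primary hypothesis is not at stake.

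**Working it through.** **Inputs**

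- Factors: 6 named (section 9.4.7).
- Endpoints: 1 primary plus the 9 secondary constructs in section 9.1 (treatment adherence, interdialytic weight gain, albumin, knowledge, self-efficacy, social support, coping, quality of life, provider communication) = 10.
- Level: 0.05, two-sided (section 9.4.1).
- Control rate, section 9.2: "we expect 0.27 events per month (100 prevalent patients and 27 composite events per month".
- Size and effect, section 9.2: "With 73 patients per group (after 25% drop-out), our study has >80% power to detect 20% reduction".
- Allocation, section 4.1: "Patients will be randomized in a 1:1 allocation".
- Follow-up: 18 months as first planned, now limited to 12, or 12 to 18 for those already further on (sections 1.1 and 1.2).

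**1. The plan's own figure.** The plan states power for the main effect only. Expected events over 18 months: 73 × 0.27 × 18 = 354.78 in controls, and × 0.80 = 283.82 under intervention. SE of the log rate ratio = √(1/354.78 + 1/283.82) = 0.0796. Power = Φ(0.2231/0.0796 − 1.96) = 80.0%; rate-difference and square-root versions give 80.2% and 80.3%. The stated power reproduces. At 12 months the same inputs give 236.52 and 189.22 events, SE 0.0975 and 63% power.

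**2. False positives if no interaction is real.** Tests: 6 × 10 = 60. Expected false positives: 60 × 0.05 = 3.0. Chance of at least one if independent: 1 − 0.95^60 = 95.4%. The endpoints are probably correlated, so this was also simulated with equal correlation between the ten endpoints within each factor:

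| Assumed correlation | Chance of at least one |
|---|---|
| 0 (exact) | 95% |
| 0.3 | 93% |
| 0.5 | 87% |
| 0.7 | 76% |

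The expected count stays at 3.0 whatever the correlation.

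Sixty is a low count. Scoring as in section 9.4.3, with two summary scores for quality of life and 14 coping subscales, gives about 26 scores: 26 × 6 = 156 tests, 7.8 expected. Alternatively, adding the 3-month comparison for the nine secondary constructs gives (10 + 9) × 6 = 114 tests, 5.7 expected. For the primary endpoint alone: 6 × 0.05 = 0.30 expected, and 1 − 0.95^6 = 26.5%.

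**3. Power and inflation on the primary endpoint.** Assume a binary factor split 50:50, one test per factor and no clustering. The SE of the log ratio of rate ratios is then twice the main-effect SE: 2 × 0.0975 = 0.195 at 12 months and 2 × 0.0796 = 0.159 at 18. Inflation is the mean absolute estimate among significant results, divided by the true log ratio.

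| True ratio | Power, 12 m | Inflation, 12 m | Power, 18 m | Inflation, 18 m |
|---|---|---|---|---|
| 0.80 | 21% | 2.2-fold | 29% | 1.8-fold |
| 0.60 | 75% | 1.16-fold | 89% | 1.06-fold |

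The reason is visible in the threshold. At 12 months an estimate must reach exp(−1.96 × 0.195) = 0.68 to be significant, so a true 0.80 can be displayed only if it is overestimated. With assumed overdispersion of 2 to 3, power at 12 months for 0.80 falls to 13% to 10%, and inflation rises to 3.0 to 3.7-fold. The documents give no standard deviations, so the same calculation cannot be done for the secondary endpoints.

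**4. Share of significant interactions that are false.** With q the share of tested interactions that are real, the false share is 0.05(1 − q) / [0.05(1 − q) + q × power]. The documents give no q, so it is varied. Powers are those for a true ratio of 0.80:

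| Assumed q | 12 m (power 21%) | 18 m (power 29%) |
|---|---|---|
| 5% | 82% | 77% |
| 10% | 68% | 61% |
| 20% | 49% | 41% |

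The false share passes one half when q is below 0.05/(0.05 + power): 19% at 12 months, 15% at 18.

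**The case against.** The plan uses formal interaction terms rather than separate p-values within subgroups, names six factors in advance, and speaks of examining potential effect modification. No efficacy decision depends on these tests. Section 9.4.1 promises CONSORT-based reporting with confidence intervals. All of this stands and limits the seriousness of the point. It does not deal with the open list, the unadjusted level or a display that depends on significance.

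Three stronger readings are tempting and are not supported:

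- A reader might infer that the displayed subgroups will be mainly false positives, or mostly noise. That needs the share of real interactions and the power to detect them, and the documents give neither. As step 4 shows, it is true for some plausible values and false for others.
- A reader might infer that non-significant interactions will be withheld. The word only does not appear. It is the natural reading of when stratified effects are shown, but the section is silent on the remaining interaction results; it does not exclude them.
- A reader might tie the whole rule to the aim in section 2.3.2 of understanding differential effects across population groups. That sentence concerns process measures at the Bronx and Nashville facilities, and of the six factors only race/ethnicity clearly matches it.

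The 95% figure is also the independent-test value and should be given with its range.

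**Conclusion.** The point holds in a limited form. Followed as written, section 9.4.7 selects subgroup estimates on significance from at least 60 unadjusted tests. About 3 false-positive interactions are expected if none is real. The chance of at least one is about 95% under independence and about 76% to 93% under assumed correlations of 0.7 to 0.3. False findings are therefore likely, and displayed effects are biased away from zero. On the primary endpoint at 12 months the inflation is about 1.2-fold for a true ratio of 0.60 and about 2.2-fold for 0.80.

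These sizes rest on 73 per group, 50:50 binary factors, one test per factor, no clustering and, unless stated, no overdispersion. The direction of the bias does not depend on them. The primary test is unaffected. This should be changed before analysis, but it does not threaten the main result.

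**What to change.** Replace the sentence that makes display conditional on significance. The new text should:

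- close the list at the six named factors, with cut points or categories fixed before analysis;
- report every subgroup estimate with its confidence interval and interaction p-value, whatever the significance;
- state the number of interaction tests, which means fixing the scores that represent each secondary construct;
- label all subgroup analyses exploratory.

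Reporting everything removes the selection that inflates displayed effects. It does not lower the number of chance findings: 60 tests still carry 3 expected. The stated count and the label let a reader allow for that.

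Limiting interaction tests to the primary endpoint is optional. It would cut the expected number to 0.30, but six tests at 0.05 would still carry a 26.5% chance of at least one false interaction, if independent.

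The cost is SAP wording, a longer table and weaker language for any subgroup finding. No new data are needed.
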